 Seventeen older (age >70 years) adults with a history of falls were recruited for a preliminary study of our MMBI. Subjects exercised 3 times/week for 16 weeks in our gymnasium followed by a four-month long home exercise regimen (adapted from the VISION 8 program) after completion of the center-based portion of the intervention. Sixteen out of 17 individuals completed all portions of the study with > 90% adherence in the 16 who completed the study. Six of the 16 fell at least once during the 4 months of the home-based phase of the study, and an additional six subjects reported at least 1 near fall. These falls and near falls did not occur during the exercise, but rather during normal daily activities. Four-square times in those who fell were significantly slower (12.7 +6.5 seconds) than in those who did not fall (6.0 + 2.1 seconds, p < 0.01). Notably, however, the slower individuals also had the greatest improvement with the intervention. After 16 weeks of center-based exercise, MMBI scores on the functional gain assessment increased by 12% and the time to complete the four-square test decreased by 24%, with even greater improvements of 40-50% for individuals whose function was most impaired at baseline. Distance covered during the six minute walk increased by 5% (p < 0.04). Maximum weight lifted during a leg press increased demonstrating significant improvements in lower extremity strength. Importantly these improvements were maintained after the four-month home-based exercise program. The subjects in this study differ from those we propose to study as the primary enrollment criteria was a history of falls, not obesity. In addition, there was no requirement that they use walking assistive devices. Nevertheless, these findings demonstrate that our multimodal intervention can be performed safely in an at risk population and improves multiple physical performance domains.
 GEROFIT cross-sectional data

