 We performed assessments of physical functioning in 24 older (> 65 years) Veterans at risk of functional and mobility decline based on their use of walking assistive devices enrolled in the GEROFIT clinical demonstration project. All of the subjects had performance-based evidence of impaired mobility. Overall the subjects had slow gait speed, poor lateral mobility and balance on the four square step test (FSST), poor endurance on the 6 minute walk test and reduced lower extremity proximal strength on the chair stands. Many of the Veterans scored below the 5th percentile on many of these measures and >50% had SPPB scores < 9. Impact of 3 months of GeroFit on functional performance in older obese Veterans: In this revised grant we provide preliminary data in 16 obese (BMI 35.8 + 5.7) older (71 + 4 years) Veterans with SPPB scores < 10 (8.5 + 1.7, mean + SD) indicative of lower extremity functional impairment who completed 3 months of GeroFit. On average these subjects had 10 medical problems and were taking 15 medications per day. After 3 months their SPPB improved from 8.5 + 1.7 to 9.56 + 2.1, the number of chair stands performed in 30 seconds increased from 7.5 + 3.7 to 8.9 + 5.4, four square step test (FSST) time an index of fall risk and lateral mobility decreased (improved) from 14.0 + 5.0 to 13.0 + 4.2 seconds and 6 minute walk distance increased from 363 + 118 yards to 418 + 122 yards. On average weight did not change in these Veterans. The exercise intervention proposed in this study will be of longer duration, with greater individualized attention with a more customized exercise progression than that employed in GeroFit.
- 4 *** Provide the scientific or scholarly background, rationale, and significance of the research and how it will add to existing knowledge:**
 Depending upon the criteria employed, it is estimated that >11 million older adults, or approximately one-third of non-institutionalized older adults have impaired mobility and >4 million older adults use walking assistive devices (1,2). It is well established that performance-based indices of impaired mobility such as slow gait speed, inability to perform the 400 m walking test and poor distance covered during the 6 minute walk test are predictive of increased mobility limitation, mobility disability, cardiovascular mortality and death.¹¹⁻¹⁴

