 The order of the tests will vary from subject to subject depending upon their schedule and the availability of the equipment.

After completion of baseline testing, participants will enter the intervention phase

Phases 3-5. Interventions and Outcome Assessments will be performed at 3 months and at 6, 12 months and a final assessment at the end of 24 months for subjects who are in the optional retention exercise program.

INTERVENTIONS

MULTIMODAL BALANCE INTERVENTION (MMBI): The MMBI has been designed to specifically address the proximal strength, balance, and mobility deficits of these severely deconditioned older obese Veterans who use assistive devices. The MMBI intervention will be conducted in the VA hospital or the VA Annex in downtown Baltimore and at the more suburban Loch Raven Community Based Outpatient Clinic. The two sites are 6 miles apart and there is routine shuttle service between them. Our MMBI will be held once a week or once every other week for an hour and will consist of a dynamic balance class (30 minutes), a supervised obstacle course (10 minutes), and lower extremity and core strengthening (20 minutes). The exercises will focus on dynamic weight shifts with an emphasis on the lateral and diagonal directions. Over time the exercises will gradually increase in difficulty. An instructor will lead each class and 1-2 assistants will be present to assist in mitigating the risk of falls. The supervised obstacle course will focus on obstacle negotiation, walking over challenging surfaces, and moving in the lateral, diagonal, and backward directions. Strength training of the lower extremities and core will focus on strengthening the major muscles of the lower extremity and core (hip flexors/extensors, hip abductors/adductors, knee flexor/extensors, ankle planter flexor/dorsiflexors, ankle invertors/evertors, and core abdominal/back extensor muscles) utilizing commonly standard gymnasium equipment, ankle weights, and body weight. If group exercise is unavailable due to COVID-19, individuals will be provided with a written home exercise program to perform or sessions via telehealth twice a week. The intervention is 3 months long with optional extension out to two years.

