SAMPLE SIZE CALCULATIONS were determined for the physical outcomes. Perera and colleagues proposed that an improvement of 19-22 meters on the 6 minute walk test (6MWD) would be clinically meaningful and an increase of 47-49 meters would be considered substantial (72). In our prior studies in subjects with impaired mobility, exercise increased 6MWD 10 to 30%. In our preliminary studies in obese mobility limited Veterans enrolled in Gerofit, the 6MWD increased by 15% (57 +/- 60 m) and the number of chair stands performed by 19%. We anticipate greater improvements with weight loss + MMBI on the order of 30 to 50 M greater improvement in MMBI + weight loss versus MMBI only. Using lower estimates, if the true difference in mean response of matched pairs is 30 +/- 50 meters, we will need to study 45 subjects in each group to be able to reject the null hypothesis with two-sided power of 0.8 and Type I error probability of 0.05. We previously reported that an exercise intervention in middle aged and older overweight and obese men increased VO2peak (L/min) by 17% with no change with weight loss (50). The study by Villareal et al. reported a 17% improvement in VO2peak in the combined group versus about 6% in the diet group. To detect a 15% difference in VO2peak between groups with a power of 0.80 and a p-value <0.05, we would need to enroll 41 subjects per group, which is close to the sample size required for the 6MWD. On a percentage basis we anticipate that there will be even more substantial improvements in lateral mobility and balance as assessed by the four square step test (FSST) than that observed for the change in usual gait speed or 6MWD. In our preliminary data, the MMBI decreased the time to complete the FSST by 24%, with the greatest improvement in the frailest subjects. Therefore, fewer subjects might be required to demonstrate a difference in the improvement in balance between groups.

We will enroll 60 subjects. Typical attrition rates are 20-25%, primarily due to the development of non-study related medical problems. This will result in 45 completers. If a greater than anticipated number of subjects fail to complete the study, we will enroll additional subjects.

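### The stated 45 per group and 80% power belong to a two-arm contrast the design no longer has; no pre-post planning gain is given, and the MMBI pilot's own 5% walk gain is left out

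*Combined protocol and SAP*

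**What the plan says.** **Planning effect** (Sample Size and Data Analysis, item 1). The anticipated effect is "30 to 50 M greater improvement in MMBI + weight loss versus MMBI only". The calculation then reads "Using lower estimates, if the true difference in mean response of matched pairs is 30 +/- 50 meters", with 45 subjects in each group needed to "reject the null hypothesis with two-sided power of 0.8 and Type I error probability of 0.05". The same item enrols 60 in total and expects 45 completers after 20–25% attrition.

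**Design** (Justification, Objective, & Research Design, item 2). All subjects now receive MMBI and nutrition. There is no MMBI-only group.

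**Background gains** (Sample Size, item 1). "In our prior studies in subjects with impaired mobility, exercise increased 6MWD 10 to 30" percent, and in GeroFit by 15% (57 ± 60 m). The item also cites a 24% fall in four square step test (FSST) time with the MMBI.

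**MMBI pilot** (Justification, item 3). "Subjects exercised 3 times/week for 16 weeks in our gymnasium"; "Distance covered during the six minute walk increased by 5% (p < 0.04"). The 24% FSST improvement is reported there too. The 5% does not appear in the sample-size item.

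**Schedule.** Study Procedures, item 1, says "Our MMBI will be held once a week or once every other week for an hour", for 3 months with an optional extension to two years. If group exercise is unavailable because of COVID-19, there is a home programme or twice-weekly telehealth. The paragraph on acute medical events, in the same item, ties postponement of an outcome assessment to completing six thrice-weekly in-center sessions. Justification, item 3, compares the plan with 3 months of GeroFit and says "The exercise intervention proposed in this study will be of longer duration".

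**The concern.** The sample-size text is the only place where the plan says what the trial can detect on its primary outcome, and it describes a comparison that cannot be made. What will be tested is the change over time in one group (Sample Size and Data Analysis, item 2, Specific aim 1). For that, the plan gives no expected gain, no SD of change chosen for the purpose, and no power or precision.

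A reader who looks for a within-group figure finds 10–30%, 15%, and 30 m labelled as a lower estimate. The one six-minute walk result for this exercise programme, 5%, lies below all the percentages cited and is missing, although the FSST figure reported for the same pilot is used. The pilot also ran at a session frequency that the current group schedule does not match. At stake is whether the stated power can be relied on and whether the planning inputs are shown in full.

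**Working it through.** **1. Reproduce the plan's figure.** Inputs from Sample Size, item 1: difference 30 m, SD 50 m, two-sided alpha 0.05, power 0.80.

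- Two independent groups, normal approximation: n = 2(1.960 + 0.842)² × (50/30)² = 43.6, so 44 per group. The noncentral t gives 45, with power 0.804. The stated 45 reproduces.
- Paired or one-sample, as the mention of matched pairs might suggest: n = (1.960 + 0.842)² × (50/30)² = 21.8, so 22, or 24 by t. This does not give 45.
- Attrition: 60 × 0.75 = 45.

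So 45 is a two-group, per-arm number. It has become the total number of completers in a single group.

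**2. What 45 completers give for a pre-post change.** One-sample t, df = 44, critical value 2.015. SD 50 m is the plan's planning value and SD 60 m is the GeroFit value; neither is the MMBI pilot's SD.

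- 95% CI half-width = 2.015 × SD/√45: 15.0 m (SD 50) or 18.0 m (SD 60).
- Change detectable with 80% power: 21.4 m or 25.7 m.
- Power at 30 m: 0.976 or 0.907.

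**3. The pilot's 5% in metres.** The pilot's baseline is not given, so a baseline has to be assumed.

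- GeroFit baseline in Justification, item 3: 363 yd × 0.9144 = 332 m; 5% = 16.6 m.
- Baseline implied by Sample Size, item 1: 57 m/0.15 = 380 m; 5% = 19.0 m.

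| True change | Power, SD 50 | Power, SD 60 |
|---|---|---|
| 16.6 m | 0.59 | 0.44 |
| 19.0 m | 0.70 | 0.55 |
| 30 m | 0.98 | 0.91 |

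The plan's own range for a meaningful change is 19–22 m. For assumed baselines of 300–450 m, 5% is 15–22.5 m, with power 0.50–0.84 (SD 50) or 0.38–0.69 (SD 60).

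**4. Sensitivity to the SD.** If the pilot's p < 0.04 came from a two-sided paired t-test on its 16 completers, and p is taken as 0.04, then t = 2.25 and mean/SD = 2.25/√16 = 0.56. With a mean of 16.6 m the SD would be about 30 m, and power with 45 completers about 0.96. The test is not named, and a p-value from so small a pilot is likely to be optimistic. The power figures in step 3 therefore depend heavily on an SD the documents do not supply.

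**5. 30 m as a fraction of baseline.** 30/332 = 9.0% and 30/380 = 7.9%: above the pilot's 5% and below the cited 10%.

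**6. Sessions.** Pilot: 3 × 16 = 48. Current group schedule over 3 months (12–13 weeks): about 12–13 if weekly, about 6–7 if every other week. Telehealth twice a week: about 24–26. None of these is the thrice-weekly frequency that the postponement rule presupposes.

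**The case against.** A reader might infer that the pilot's 5% shows 30 m to be too large. The documents do not support that. The 30 m is the bottom of a 30–50 m between-arm range, the extra gain from adding weight loss to MMBI. The 10–30%, 15% and 5% are within-group gains, so a 5% gain on MMBI alone neither confirms nor refutes an increment over MMBI.

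Even read as a pre-post gain, 30 m lies below the GeroFit result (55 yards, or 50 m, in Justification, item 3; 57 m in the sample-size item). GeroFit is the closer population: obese older Veterans with lower-extremity impairment. The MMBI pilot had 17 subjects aged over 70, selected for falls rather than obesity, and was exercise only. The current programme adds a hypocaloric component for which the documents give no walk-distance effect. All of this stands. It leaves 30 m unsupported, not refuted.

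Two further inferences also fail. Power of 44–59% at 16.6 m should not be read as the trial's true power, because it pairs the pilot's gain with SDs from elsewhere (step 4). And a small change would not automatically count as failure: no success threshold at 30 m is set, the analysis is repeated measures ANOVA at two-sided 0.05, and the plan itself calls 19–22 m meaningful.

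On dose, the documents give no dose-response for walk distance, so the lower session count cannot be turned into a smaller expected gain. The longer-duration statement is defensible if the optional extension counts. The pilot's 5% is also openly disclosed in the background section. Its absence from the sample-size item is a gap in the argument, not concealment.

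**Conclusion.** The point holds in a limited form. The 45 per group and 80% power are arithmetically correct for two independent arms, but that contrast has been dropped and the statement no longer describes the trial. No within-group planning gain replaces it. Calling 30 m a lower estimate of the single-arm change has no support in the documents, which contain a smaller MMBI figure that the sample-size item omits; nor do they show 30 m to be too high.

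For the change actually tested, 45 completers give adequate power at 30 m on either SD. At the pilot's gain the answer ranges from about 44% to about 96%, depending on an assumed baseline and on an SD that is not reported. The honest summary is the precision: about ±15 to ±18 m.

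Separately, the session-frequency and duration statements do not agree with one another. The postponement rule rests on in-center sessions at a frequency that the schedule does not provide.

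**What to change.** In Sample Size and Data Analysis, item 1:

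- Replace the two-group statement with the pre-post precision for 45 completers: 95% CI half-width about 15 m (SD 50) or 18 m (SD 60), detectable change about 21 m or 26 m at 80% power, and power at 30 m and at 17–19 m as tabulated. State that the pilot's baseline and SD are not given, and that its p-value, if from a paired t-test, would imply a smaller SD and higher power.
- List the MMBI pilot's 5% beside the 10–30% and GeroFit 15% figures, noting the differences in population and intervention, and drop the lower-estimate wording.

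In Justification, item 3, and Study Procedures, item 1, reconcile the statements on duration and session frequency, including the postponement rule's reliance on thrice-weekly in-center sessions. Which schedule applies is for the investigators to settle.

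The cost is rewording only. No subjects are added and the analysis is unchanged. The power statement improves at 30 m and becomes less certain at the low end.

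### The pilot six-minute-walk gain is given as 57 m in one place and works out at 50 m in another, and the sample size uses an SD of 50 m, without a reason, where the cited pilot SD is 60 m

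*Combined protocol and SAP*

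**What the plan says.** The Sample Size and Data Analysis section, item 1, summarises preliminary work in obese, mobility-limited GeroFit Veterans: "the 6MWD increased by 15% (57 +/- 60 m"), and "the number of chair stands performed by 19" per cent. It then bases the calculation on different values, "if the true difference in mean response of matched pairs is 30 +/- 50 meters", and concludes that "we will need to study 45 subjects in each group" with "two-sided power of 0.8 and Type I error probability of 0.05". The same item plans to enrol 60, expects 20-25% attrition and counts on 45 completers. It takes 19-22 m as a clinically meaningful improvement.

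The Justification, Objective, & Research Design section, item 3, describes the pilot in more detail: "In this revised grant we provide preliminary data in 16 obese (BMI 35.8 + 5.7) older (71 + 4 years) Veterans" who completed 3 months of GeroFit. There, "6 minute walk distance increased from 363 + 118 yards to 418 + 122 yards", and "the number of chair stands performed in 30 seconds increased from 7.5 + 3.7 to 8.9 + 5.4". That section labels its plus-or-minus values as mean and SD. Item 2 of the same section states that every subject now receives the combined intervention, so there is no comparison group.

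**The concern.** Two separate things need attention.

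- **The gain.** If both sections describe the same Veterans, the gain in metres should follow from the yards by conversion, and it does not. The sample-size text uses the pilot gain as the background against which it anticipates larger improvements.
- **The SD.** The calculation uses a smaller SD than the pilot value quoted a few lines above it, with no explanation. A smaller SD lowers the required number and raises the stated power.

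The six-minute walk distance is the primary outcome. When the sample-size statement is rewritten for the present single-group design, it will need an SD of change. The 60 m figure is the only pilot one the documents offer.

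**Working it through.** **Inputs.** Pilot means 363 and 418 yards, with SDs 118 and 122 yards and n = 16 (Justification, item 3). Cited gain 15%, 57 m, spread 60 m; planning difference 30 m, SD 50 m; two-sided alpha 0.05; power 0.80; 45 per group; 45 completers (Sample Size, item 1). One yard is 0.9144 m.

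**1. The pilot gain.**
- Difference: 418 - 363 = 55 yards; 55 x 0.9144 = 50.3 m.
- Relative: 55 / 363 = 15.2%, matching the cited 15%.
- Rounding limits: (417.5 - 363.5) x 0.9144 = 49.4 m to (418.5 - 362.5) x 0.9144 = 51.2 m. Rounding does not reach 57 m.
- 57 m against that baseline: 363 x 0.9144 = 331.9 m, and 57 / 331.9 = 17.2%.
- A mislabelled unit does not resolve it: 57 yards is not 55 yards, and 57 / 363 = 15.7%.
- Link between the sections: chair stands (8.9 - 7.5) / 7.5 = 18.7%, matching the cited 19%.

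**2. What the 60 m is.** Read as an SD of change, 60 m is 60 / 0.9144 = 65.6 yards. With the pilot SDs, the implied pre-post correlation is (118² + 122² - 65.6²) / (2 x 118 x 122) = 0.85, which is plausible. Read as a standard error with n = 16, it would imply an SD of 60 x √16 = 240 m, which is not.

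**3. Reproducing the plan's 45 per group.** Two-sample normal approximation: n = 2 x (1.96 + 0.842)² x (50/30)² = 43.6, or 44. The two-sample t-test gives 44.6, or 45, with power 0.80 at 45 per group. A paired or one-sample t-test, which the reference to matched pairs might suggest, gives 23.8, or 24, and does not reproduce the figure. So 50 m acts as a within-group SD of change, the same kind of quantity as the pilot 60 m.

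**4. The same formula at SD 60 m.** Normal approximation: 2 x (1.96 + 0.842)² x (60/30)² = 62.8, or 63; t-test 63.8, or 64 per group. Power at 45 per group is 0.65.

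**5. The design as it now stands: one group, 60 x (1 - 0.25) = 45 completers, one-sample t-test on change.** The half-width is t(0.975, 44 df) x SD / √45, with t = 2.015.

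| Quantity | SD 50 m | SD 60 m |
|---|---|---|
| Power, 30 m change | 0.98 | 0.91 |
| Power, 20 m change | 0.75 | 0.59 |
| Change detectable with power 0.80 | 21.4 m | 25.6 m |
| 95% CI half-width | 15.0 m | 18.0 m |

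At SD 50 m the detectable change lies inside the plan's 19-22 m range; at SD 60 m it lies above it.

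**The case against.** Several points on the other side stand.

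- **Same sample.** The text never says that the two sections describe the same Veterans. The sample-size item gives no n and speaks of studies in the plural, and 57 m is exactly 15% of 380 m, so it would be consistent with another subset. The matching 15% and 19% make a single source likely but do not prove it. A reader might infer that 57 m is simply an error for 50 m; the documents cannot show which figure is wrong.
- **Lower estimates.** A reader might take this phrase in the sample-size text as a claim that the SD is conservative too. It follows directly on an anticipated range of 30 to 50 m, so it most naturally refers to choosing 30 m, which is conservative. No range is given for the SD.
- **Is 50 m too small?** With n = 16 and normality, the 95% interval for an SD of 60 m is 60 x √(15/27.49) to 60 x √(15/6.26), about 44 to 93 m. An SD of 50 m is compatible with the pilot. The gap is a missing justification, not a demonstrated error.
- **Underpowered trial.** A reader might infer from 64 per group, or from power 0.65, that the trial is too small. Those figures concern a comparison that is no longer made. For one group and a 30 m change, power remains above 0.90 at either SD.
- **Effect of the 57 m.** It does not enter the formula and changes neither the sample size nor the power.

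What remains is an unreconciled pilot gain and a planning SD below the only cited pilot value, without a reason.

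**Conclusion.** The point holds in this form. The two accounts of the pilot gain, 57 m and 50.3 m, disagree if they describe the same data, and must be reconciled; by itself this is a reporting inconsistency. The more useful part is the SD: the stated 45 per group at power 0.80 depends on 50 m, for which no source is given, while the same paragraph cites 60 m.

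For the present design the consequence is moderate. Power is still ample for 30 m. For a change in the 19-22 m range that the plan itself calls meaningful, the choice of SD matters: at 20 m it lowers power by 0.16.

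This rests on reading the pilot spread as an SD of change in metres, as printed; on 45 completers; on a one-sample t-test of change; and on the GeroFit SD carrying over to this intervention and population.

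**What to change.** 1. Check the pilot gain and its SD against the source data, and make the two sections agree. If the 57 m comes from a different set of Veterans, say so and give its n.
2. Report both values in metres, and label the spread as the SD of change.
3. In the restated one-group power or precision statement, use the verified pilot SD (60 m as printed), or keep 50 m and give its source. Showing both values would make the dependence on the SD plain.

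The cost is a check of the pilot data and a few corrected figures. No participants are added. If 60 m is confirmed, the stated power and precision become slightly less favourable.
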